## ABSTRACT

**Rationale:** Men who have sex with men (MSM) continue to be disproportionately affected by HIV. The majority of HIV infections among MSM occur through exposure to the rectal mucosa during condomless receptive anal intercourse (CRAI). To aid in prevention, pre-exposure prophylaxis (PrEP) and post-exposure prophylaxis (PEP) are recommended for MSM who may be exposed to HIV. Current recommendations for PrEP are to take the combination anti-HIV drug, tenofovir+emtricitabine (TDF/FTC), on a daily basis for the duration of someone's HIV risk exposure period which could be months or years. For PEP, a three-drug anti-HIV medication is recommended within 72 hours of a possible exposure for a 28-day course. While PrEP and PEP are efficacious, both the daily dosing of PrEP and the 28 day course of PEP limit their utility in practice as many users find long term adherence to these regimens to be difficult. Therefore, additional short-course dosing regimens for PrEP and PEP are being considered for future development. This proposal seeks to understand how other anti-HIV medications, taken around the time of HIV exposure (peri-PrEP), are absorbed into different body compartments, including mucosal tissues, as they may be considered for peri-PrEP regimens in the future. The study drug provided in this study will not protect participants from HIV or treat any active infection.

**Design:** To address the absorption of anti-retroviral drugs by mucosal tissues in MSM, investigators at Emory University will collaborate with the Center for Disease Control and Prevention (CDC) to conduct a clinical trial of up to 62 MSM aged 18-49 with measurement of anti-retroviral drug concentrations in various body compartment sites of possible HIV exposure. We plan to enroll men who are HIV negative that engage in receptive anal intercourse (RAI) and are not currently (or have no current plans) taking PEP or pre-exposure prophylaxis (PrEP). We will enroll participants in Pre-drug arm (control) first. After the completion of pre-drug arm, we will then begin enrollment sequentially in Arm A, followed by Arm B and finally Arm C. Arms A, B, and C will be broken down into two (2) different sub-groups, which will determine the timing of when the participant will undergo a rectal swab and biopsy procedure (Arm A: groups A.1 and A.2; Arm B: groups B.1 and B.2; and Arm C: groups C.1 and C.2). Arm D will include a single time point specimen collection. We will recruit participants through existing research databases at the Hope Clinic and the Rollins School of Public Health, Research Match, and Clinical Data Warehouse. Internet and paper advertisements, and community venues will also be used. At the first study visit, eligibility will be determined and screening blood work (approximately 15 mL), including a rapid HIV test, will be performed. At the second study visit, participants will be provided with a single dose of Genvoya® (fixed-dose combination anti-retroviral drug containing tenofovir alafenamide, emtricitabine, elvitegravir, and cobicistat), and instructed to take the dose at home with documentation by digital, time-stamped photo or video. At the third study visit, which will occur at the Hope Clinic 24hrs after home dosing, participants will be given another single dose of Genvoya. Depending on which study arm the participant is

sequentially assigned to, the participant will be asked to return to the Hope Clinic at different time points to complete the remaining visits (visit 4 and visit 5). During visits 4 and 5, all participants will undergo blood collection (approximately 24 mL of blood will be obtained), an oral cheek swab, urethral swab, 1 pre-wet and 1 dry penile swabs, and a urine sample will be collected, some of which will be used for STI testing. Each participant will also undergo a single time-point (depending on study arm assignment—either visit 4 or 5) rectal secretion collection with swabs and wicks, a swab for rectal STI testing, and a rectal biopsy via rigid sigmoidoscopy. All participants will be asked to abstain from receptive anal intercourse for 7 days after biopsy procedures to allow the mucosa to heal.

Participants will also be asked to provide an optional single semen specimen on the day of rectal sampling to further evaluate drug levels. All biologic specimens will be transferred to CDC within 4 hours of collection for measurement of antiretroviral drug levels.

Participants may participate in more than one study arm; however, at least 6 weeks must lapse after completion of 1 study arm before entry into another. Men who participate in more than one arm will not be consented again and do not have to repeat the screening visit (visit 1) when starting another arm; they will begin the new arm at visit 2.

**Duration:** The duration of this study is 2 years. Participants will be considered ‘on-study’ for no more than 12 weeks.

**Sample size:** For this protocol we will recruit 62 HIV-negative MSM (age 18- 49) who meet eligibility criteria outlined in the protocol.

**Population:** The population to be studied in this protocol are healthy HIV negative MSM who are engaging in receptive anal intercourse (RAI) and are willing to perform study procedures. We will recruit participants through existing research databases at the Hope Clinic and the Rollins School of Public Health, through internet and paper advertisements, and community venues as is currently the process for [name] ongoing research protocols.

### **LAY SUMMARY:**

Men who have sex with men (MSM) continue to be disproportionately affected by HIV. In 2014, MSM made up approximately 2% of the U.S. population but accounted for 70% of the new HIV infections (CDC)(2). The majority of MSM acquire HIV after exposure to the rectal mucosa through unprotected receptive anal intercourse. Pre-exposure prophylaxis (PrEP) and post-exposure prophylaxis (PEP) are recommended for MSM who may be exposed to HIV to prevent infection. Current recommendations for PrEP are to take the combination anti-HIV drug, tenofovir+emtricitabine (TDF/FTC), on a daily

basis for the duration of someone's HIV risk exposure period which could be months or years. For PEP, a three-drug anti-HIV medication is recommended within 72 hours of a possible exposure for a 28-day course. While PrEP and PEP are effective, some people find it difficult to follow the recommended regimen. Therefore, additional short-course dosing regimens for PrEP and PEP are being considered for future development. The study drug provided in this study will not protect participants from HIV or treat any active infection. This proposal seeks to understand how other anti-HIV medications, taken around the time of HIV exposure (peri-PrEP), are absorbed into different body compartments, including mucosal tissues, as they may be considered for peri-PrEP regimens in the future.

For this protocol, we will recruit 62 HIV-negative MSM aged 18-49. We plan to complete enrollment for the pre- drug (control) arm first. After the completion of the pre- drug arm, we will continue to enroll sequentially in each arm until all arms are filled (Pre-drug, then Arm A, then Arm B, then Arm C, then Arm D). All participants will provide written informed consent at the first study visit and undergo a screening medical history, physical exam, and safety laboratory tests. All biologic specimens collected will be transferred to CDC on the day of collection for measurement of drug levels.

Participants (up to n=6) enrolled in the pre-drug arm will not receive any drug. At visit 2, they will undergo blood, urine, penile swab, cheek swab, rectal swab and rectal biopsy collection.

Participants (up to n=16) enrolled in Arm A will be provided with a single dose of Genvoya®, at study visit 2, and instructed to take the dose at home which they will document with a smartphone photo or video time/date stamp. Participants will return to the clinic 24hrs after taking home dose for visit 3 when participants will be given another single dose of Genvoya. Specimen collection including blood, urine, urethral swab, penile swab, and cheek swab will be collected 2hrs after taking the medication in the clinic (visit 4), and 48hrs after taking the medication in the clinic (visit 5). In addition, participants will be sequentially assigned to undergo rectal swab and biopsy procedure at a single time point, at visit 4 (sub-group A.1) OR visit 5 (sub-group A.2). Participants will also be asked to provide an optional semen specimen within 2hrs of their biopsy procedure to further evaluate drug levels. All participants will undergo only one rectal swab and biopsy procedure.

Participants (up to n=16) enrolled in Arm B will be provided with a single dose of Genvoya®, at study visit 2, and instructed to take the dose at home which they will document with a smartphone photo or video time/date stamp. Participants will return to the clinic 24hrs after taking home dose for visit 3 when participants will be given another single dose of Genvoya. Specimen collection including blood, urine, urethral swab, penile swab, and cheek swab will be collected 4 hours after taking the medication in the clinic (visit 4), and 72hrs after taking the medication in the clinic (visit 5). In addition,

TITLE OF PROJECT: On-Demand PEP  
Emory IRB  
PRINCIPAL INVESTIGATOR: [name], MPH

participants will be sequentially assigned to undergo rectal swab and biopsy procedure at a single time point, at visit 4 (sub-group B.1) OR visit 5 (sub-group B.2). Participants will also be asked to provide an optional semen specimen within 2hrs of their biopsy procedure to further evaluate drug levels. All participants will undergo only one rectal swab and biopsy procedure.

Participants (up to n=16) enrolled in Arm C will be provided with a single dose of Genvoya®, at study visit 2, and instructed to take the dose at home which they will document with a smartphone photo or video time/date stamp. Participants will return to the clinic 24hrs after taking home dose, for visit 3, at which time, participants will be given another single dose of Genvoya. Specimen collection including blood, urine, urethral swab, penile swab, and cheek swab will be collected 24hrs after taking the medication in the clinic (visit 4), and 96hrs after taking the medication in the clinic (visit 5). In addition, participants will be sequentially assigned to undergo rectal swab and biopsy procedure at a single time point, at visit 4 (sub-group C.1) OR visit 5 (sub-group C.2). Participants will also be asked to provide an optional semen specimen within 2hrs of their biopsy procedure to further evaluate drug levels. All participants will undergo only one rectal swab and biopsy procedure.

Participants (up to n=8) enrolled in Arm D will be provided with a single dose of Genvoya®, at study visit 2, and instructed to take the dose at home which they will document with a smartphone photo or video time/date stamp. Participants will return to the clinic 24hrs after taking home dose, for visit 3, at which time, participants will be given another single dose of Genvoya. Specimen collection including blood, urine, urethral swab, penile swab, and cheek swab will be collected 8hrs after taking the medication in the clinic (visit 4). All participants assigned to Arm D will undergo rectal swab and biopsy sampling at 8hrs after taking the medication in the clinic. Participants will also be asked to provide an optional semen specimen within 2hrs of their biopsy procedure to further evaluate drug levels. All participants will undergo only one rectal swab and biopsy procedure.

After collection, biologic specimens will be picked up by the CDC and immediately transported to the Division of HIV/AIDS Prevention Laboratory Branch for processing. The lab at CDC will measure the levels of tenofovir alafenamide, emtricitabine, elvitegravir, and cobicistat in the different biologic specimens. Comparison of assay results between the study arms will help in determining the ability of the different anti-HIV drugs to be taken up by different body tissues, including at the site of possible HIV exposure.

## PROJECT DESCRIPTION

TITLE OF PROJECT: On-Demand PEP  
Emory IRB  
PRINCIPAL INVESTIGATOR: [name], MPH

**Public Health Relevance:** Information about new anti-HIV agents and how they are absorbed by different body sites will better inform scientists about the potential of new agents to be used around the time of HIV exposure---peri-PrEP.

**Goal:** To assess the pharmacokinetics and tissue distribution of anti-HIV drugs after taking a single dose of Genvoya®.

### STUDY POPULATION

A total of up to 62 HIV-negative MSM aged 18-49 will be recruited from existing Emory University study databases of MSM who have agreed to future contact about research opportunities. We will also recruit men from community engagement events conducted by Hope Clinic recruiters, from print and on-line advertisements, and from social media. Research recruiters at the Hope Clinic are experienced in recruiting this population for research studies, including those with rectal biopsies, and do not anticipate problems. [name] has conducted several similar studies before and does not anticipate any problems with recruiting the target population. Based on our previous studies, we expect a percentage of men will not complete all study visits, therefore the sample size of up to 62 men will likely result in study completion for 31 men.

### INCLUSION CRITERIA FOR MSM

- 1) HIV-negative man who reports receptive anal sex with another man in the last 6 months
- 2) Aged 18-49 years
- 3) Not currently taking PrEP and no plans to initiate during study
- 4) Not currently taking PEP
- 5) Able to provide informed consent in English
- 6) No plans for relocation in the next 3 months
- 7) Willing to undergo peripheral blood, penile swabs, urine, and rectal biopsy sampling
- 8) Willing to use study products as directed
- 9) Willing to abstain from receptive anal intercourse 3 days prior to starting study product and for the duration of the study and for 7 days after any rectal biopsy procedure.
- 10) Hepatitis B surface antigen (HBsAg) must be negative (screening lab test)
- 11) Creatine clearance >60 ml/min

### EXCLUSION CRITERIA

TITLE OF PROJECT: On-Demand PEP

Emory IRB

PRINCIPAL INVESTIGATOR: [name], MPH

- 1) History of inflammatory bowel disease or other inflammatory, infiltrative, infectious or vascular condition involving the lower gastrointestinal tract that, in the judgment of the investigators, may be worsened by study procedures or may significantly distort the anatomy of the distal large bowel
- 2) Currently infected with hepatitis virus and/ or have liver disease
- 3) Current or chronic history of kidney disease
- 4) Significant laboratory abnormalities at baseline visit, including but not limited to:
  - a) Hgb  $\leq$  10 g/dL
  - b) PTT  $>$  1.5x ULN or INR  $>$  1.5x ULN
  - c) Platelet count  $<$ 100,000
  - d) Creatinine clearance  $<$ 60
  - e) HBsAg reactive
- 5) Any known medical condition that, in the judgment of the investigators, increases the risk of local or systemic complications of endoscopic procedures or pelvic examination, including but not limited to:
  - a) Uncontrolled or severe cardiac arrhythmia
  - b) Recent major abdominal, cardiothoracic, or neurological surgery
  - c) History of uncontrolled bleeding diathesis
  - d) History of colonic, rectal, or vaginal perforation, fistula, or malignancy
  - e) History or evidence on clinical examination of ulcerative, suppurative, or proliferative lesions of the anorectal mucosa, or untreated sexually transmitted disease with mucosal involvement
- 6) Continued need for, or use during the 14 days prior to enrollment, of the following medications:
  - a) Aspirin or more than 4 doses of NSAIDs
  - b) Warfarin, heparin (low-molecular weight or unfractionated), platelet aggregation inhibitors, or fibrinolytic agents
  - c) Any form of rectally administered agent besides lubricants or douching used for sexual intercourse
- 7) Continued need for, or use during the 90 days prior to enrollment, of the following medications:
  - a) Systemic immunomodulatory agents
  - b) Supraphysiologic doses of steroids (short course steroids less than 7 days duration, allowable at the discretion of the investigators)
  - c) Experimental medications, vaccines, or biologicals
- 8) Intent to use HIV antiretroviral pre/post-exposure prophylaxis (PrEP or PEP) during the study, outside of the study procedures
- 9) Symptoms of an untreated rectal sexually transmitted infection (e.g. rectal pain, discharge, bleeding, etc.)
- 10) Current use of hormonal therapy
- 11) Any other clinical condition or prior therapy that, in the opinion of the investigator, would make the patient unsuitable for the study or unable to comply with the study requirements.

TITLE OF PROJECT: On-Demand PEP  
Emory IRB  
PRINCIPAL INVESTIGATOR: [name], MPH

12) Participants taking potent inhibitors (e.g. itraconazole, diltiazem) or inducers (e.g. rifampin, phenytoin) of the CYP3A4 enzyme that also metabolizes Genvoya will be excluded from the study.

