**Arm D (n=8; enrollment will close once 4 men complete their biopsy visit):**

**Visit 1 (screening):** Eligible MSM will provide written informed consent, be questioned about their medical history, undergo a physical exam (conducted by a study clinician) a rapid HIV test, and a peripheral blood sample for a complete blood count, creatinine, coagulation test, and hepatitis B. Participants will then be asked to return within 1- 6 weeks for visit 2.

**Visit 2:** Participants will be given a one- day supply of Genvoya®. Staff will provide instructions to participant on when to take dose at home. Participants will be asked to dose **24hrs before visit 3** and will be instructed to videotape or photograph themselves taking dose with the timestamp included. Study staff will instruct participants to bring the video/photo to their next visit to provide proof of dosing. Participants will also have the option to send a text to a specified number with the time and date of dose if their phone device does not have video capabilities.

**Visit 3:** Visit 3 takes place 24hrs after home dose. During this visit, drugs will be dispensed to participants, and they will be instructed to take one dose of Genvoya®. Men will be dosed on-site (time of dose will be recorded) and asked to return in 8hrs. Procedures should be done as close to 8hrs as possible with a +/- 1 hour window.

**Visit 4:** Visit 4 takes place 8hrs (+/- 1 hour) after on-site dose. Approximately 24 mL of blood will be drawn, an oral cheek swab, 1 pre- wet penile swabs and 1 dry penile swab, and a urethral swab will be collected. After previous swab collections are complete, participants will be asked to provide a urine sample, some of which will be used for gonorrhea and chlamydia testing, then the practitioner (Principal investigator or Co- investigator) will collect rectal secretion samples by using two swabs and insert an aptima swab for rectal gonorrhea and chlamydia testing, before the participant undergoes a rectal biopsy via rigid sigmoidoscopy.

Participants will be asked to provide an optional single semen sample, which will be collected at home, no more than 2hrs before/after the biopsy visit.

All participants will be asked to abstain from receptive anal intercourse for three days prior to drug dosing and during the study protocol in order to limit additional exposures (e.g. semen, douching, additional lubricants) to the rectal mucosa.

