All rectal biopsies will be performed utilizing a disposable rigid sigmoidoscope, light source, and jumbo biopsy forceps. [name] was trained in office based rectal biopsy procedures by [name], an experienced gastroenterologist at Emory University. All biopsies will be completed by either the PI or a delegated, licensed medical professional whom the PI has trained in the procedure. All biopsy procedures will be performed in an examination room at the Hope Clinic with assistance from the project coordinator or clinical research nurse. Similar procedures have been performed by [name] >300 times for other research protocols with no complications. Briefly, without the administration of any previous enemas or other preparation, 8-10 adequate ~1.0 mm thick biopsy specimens will be taken from normal-appearing rectal mucosa 10 cm above the external anal aperture using a rigid sigmoidoscope and flexible sigmoidoscopic forceps mounted on a semi-flexible rod. All biopsy specimens will be coded with a unique numeric identifier such that the CDC laboratories that receive the

TITLE OF PROJECT: On-Demand PEP  
Emory IRB  
PRINCIPAL INVESTIGATOR: [name], MPH

specimens will be unable to link them back to the study participants. Specimens will be transported directly to CDC after the study visit.

Twenty-four to forty-eight hours after the procedure, study personnel will contact the subjects who donated rectal biopsy samples and inquire about symptoms, complications, or adverse events related to study procedures. Subjects who report symptoms suggestive of any significant complications will receive advice on seeking care, and will be given referrals to appropriate healthcare professionals as needed. This follow-up may be completed over the phone or through electronic communication.

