Acquisition of HIV drug resistance is a theoretic concern for HIV positive people taking intermittent dosing of anti-HIV medication. For this protocol, we will test men for HIV at study entry and monitor clinically for high-risk behavior or any signs of acute HIV infection at study visits. If high risk behavior (e.g. unprotected anal intercourse with a man of unknown HIV status) or symptoms of acute HIV infection are reported, and HIV antibody test will be repeated and the participant will be counseled about the need for any follow-up testing. Clinical signs and symptoms of acute HIV infection that will be queried include: fever, fatigue, malaise, skin rash, swollen glands, oral/genital ulcers, myalgia/arthritis(3). [name] will review all reports of clinical signs/symptoms to determine appropriate follow-up and linkage to care as necessary. If a diagnosis of acute HIV infection is thought to be possible or determined by repeat HIV testing, the participant will be discontinued from the study. For this protocol, we will test men for HIV at study entry and monitor clinically for high-risk behavior or any signs of acute HIV infection at study visits.

TITLE OF PROJECT: On-Demand PEP

Emory IRB

PRINCIPAL INVESTIGATOR: [name], MPH

Men will be asked to abstain from receptive anal intercourse for three days prior to drug dosing and during the study protocol in order to limit additional exposures (e.g. semen, douching, additional lubricants) to the rectal mucosa. Men taking Genvoya® will be counseled that they should not expect to achieve protection from HIV infection by taking drug during this study, as they will be provided a limited supply. All men included in the study that have an interest in taking PrEP for HIV prevention, will be referred to an area PrEP provider at the termination of the study. The Hope Clinic has compiled a resource sheet of area providers that will be distributed to interested participants.

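### The pre-sampling rule restricts only receptive intercourse, although its stated purpose includes limiting douching and lubricant; no visible instruction covers those products, and the three-day clause has no starting event in the undosed arm

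*Combined protocol and SAP*

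**What the plan says.** The abstinence rule appears three times.

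- Inclusion criterion 9: "Willing to abstain from receptive anal intercourse 3 days prior to starting study product and for the duration of the study". It also covers the 7 days after any biopsy.
- The paragraph for all participants that closes the Arm D visit schedule asks men to "abstain from receptive anal intercourse for three days prior to drug dosing and during the study protocol in order to limit additional exposures". The exposures in mind follow in brackets: "e.g. semen, douching, additional lubricants) to the rectal mucosa".
- The Risk of Genvoya section repeats it: "Men will be asked to abstain from receptive anal intercourse for three days prior to drug dosing and during the study protocol", with the same purpose.

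Four other places bear on rectal products or on comparable instructions.

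- Exclusion criterion 6 opens "Continued need for, or use during the 14 days prior to enrollment, of the following medications", and item c lists "Any form of rectally administered agent besides lubricants or douching used for sexual intercourse".
- The rectal biopsy procedures state that specimens are taken "without the administration of any previous enemas or other preparation".
- The paragraph after the Arm D schedule tells men to keep everything out of the rectum, but only for the 7 days following biopsy.
- The semen collection section sets a product rule before collection: no lubricant or saliva on the penis for at least 48 hours.

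The pre-drug arm receives no drug and is sampled at visit 2, which falls 1 to 6 weeks after screening.

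**The concern.** The protocol names douching and lubricant as exposures to keep away from the rectal mucosa, then relies on abstinence from intercourse to achieve it. A man can follow the rule exactly and still rinse at home before a scheduled rectal examination.

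Rectal secretion is collected on two swabs and assayed for drug. If a rinse removes or dilutes surface drug, a low swab value could reflect hygiene rather than drug distribution. Each man has one rectal sampling visit per arm, so there is no within-person value to check it against. Each post-dose time point closes at 4 completed biopsy visits, so a single altered sample carries a quarter of the weight.

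The second issue is the start of the rule. Three days are counted back from the study product, an event that does not occur in the pre-drug arm.

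**Working it through.** The plan has no figure of its own on this point. The check is a comparison of text, a schedule calculation and an illustrative sensitivity.

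**1. What is restricted before sampling.** All three statements of the rule restrict receptive anal intercourse. Two of them give limiting douching and lubricant as part of the purpose. None restricts the products themselves. The instruction to keep everything out of the rectum starts after biopsy, so it cannot protect the sample. The no-enema wording describes how biopsies are done and is not addressed to participants. The semen section shows that the protocol does write product-level rules before collection, and does so for an optional specimen. The mandatory rectal specimens have no equivalent in the visible text.

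**2. Intervals covered, at nominal times.** The doses are 24 h apart. Rectal sampling is 2 h (group A.1) to 96 h (group C.2) after the on-site dose.

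- Three days counted back from the home dose: intercourse is excluded for 72 + 24 + 2 = 98 h to 72 + 24 + 96 = 192 h before sampling.
- Three days counted back from the on-site dose: 72 + 2 = 74 h to 72 + 96 = 168 h.
- Pre-drug arm: the three-day part gives no interval, because there is no dose. The part covering the whole study gives about 1 to 6 weeks, assuming it starts at screening; the protocol does not define the start.
- Interval free of douche or lubricant: not stated in any arm.

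**3. Visits exposed.** Post-dose rectal sampling takes place at 2, 4, 8, 24, 48, 72 and 96 h. That is 7 time points × 4 men = 28 planned visits. The 3 pre-drug completers bring the total to 31, the completion figure in the Study Population section. The pre-drug visits are left out of the count because a rinse cannot remove drug that was never given.

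**4. Illustrative sensitivity.** Assume that a rinse removes a fraction *f* of secretion drug in *m* of the 4 men, and that the time point is summarised by a geometric mean. The mean log concentration shifts by (*m*/4) × ln(1 − *f*), so the geometric mean is multiplied by (1 − *f*)^(*m*/4).

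| Assumed removal *f* | *m* = 1 | Fall | *m* = 2 | Fall |
|---|---|---|---|---|
| 25% | 0.75^0.25 = 0.931 | 7% | 0.75^0.5 = 0.866 | 13% |
| 50% | 0.50^0.25 = 0.841 | 16% | 0.50^0.5 = 0.707 | 29% |
| 90% | 0.10^0.25 = 0.562 | 44% | 0.10^0.5 = 0.316 | 68% |

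The removal fractions, the number of men and the choice of geometric mean are all assumptions. The visible text supplies none of them.

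**The case against.** A reader might infer from exclusion 6c that douching is allowed right up to the swab. The documents do not support that. The item is an entry criterion about need or use in the 14 days before enrollment, and it exempts only products used for intercourse. In a population selected for recent receptive anal sex, an entry rule without that exemption could exclude many eligible men. It says nothing about the period before sampling. The abstinence paragraphs and the no-enema wording also point against douching. The gap is one of silence.

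A reader might also infer that the control arm has no abstinence rule. It has one: the rule runs for the whole study and is addressed to all participants. That arm lacks only a start for the three-day clause, and a rinse there has no drug to dilute.

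Three further objections have force. Men who abstain from intercourse have less occasion to douche or use lubricant. The case report forms are not in the documents and the consent pages were removed, so a question or instruction may exist there; its absence cannot be asserted. The sensitivity concerns secretion on swabs, whereas the objective in Figure 1 is mucosal tissue, also sampled by biopsy, for which no effect is quantified.

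What remains is that the protocol's own rule does not do what the protocol says it is for, and the visible text contains nothing that closes the gap.

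**Conclusion.** The concern holds as a gap in the pre-sampling instruction. The protocol limits douching and lubricant only indirectly, through abstinence from intercourse, and states no product-free interval before rectal swabs and biopsy. The three-day clause has no anchor in the pre-drug arm.

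Up to 28 planned post-dose rectal visits are open to the problem. That counts visits without a visible instruction; it does not estimate how many would be affected. The size of any effect on rectal drug levels cannot be judged from the documents. The 7%, 16% and 44% falls for one affected man in four show how sensitive a four-man time point is under assumed removal fractions, and should not be read as predicted bias. The change is still worth making, because it is cheap and protects a measurement that rests on four men per time point.

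**What to change.** Reconcile inclusion criterion 9, the paragraph for all participants after the Arm D schedule, and the matching paragraph in the Risk of Genvoya section, as follows.

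1. Extend the pre-sampling instruction so that it covers participants' own use of rectal douches, enemas, lubricants and other rectal products as well as receptive intercourse, over the same interval and until the rectal specimens are collected. The existing rule for the 7 days after biopsy stays.
2. For the pre-drug arm, count the three days back from visit 2.
3. At the biopsy visit, ask for and record the last rectal product use. Flag affected swab results and give a sensitivity summary for each time point without them.

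Leave exclusion 6c unchanged, since it does not govern this period. Do not rely on rescheduling: the contingency visit section keeps additional visits inside the existing windows, which are ±1 hour around each post-dose time point, so recording and flagging is the workable remedy.

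The cost is a minor burden on participants, one extra case report form question and an occasional flagged result. No dose or sampling time changes.
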